8. Community rates of COVID based on 7 day moving average.

Power/Sample Size

Personal Contacts (12-14 month & 4-year-olds) Trial:

We based our hypotheses (see table, below) on a systematic review's pooled estimates of effect size for automated messages and personalized calls finding 37% and 40% of children, respectively, completed immunizations.¹ Because of the significant cost involved in making personal contacts, the minimal difference in outcome that would make it worth the effort is high.

Hypotheses	% of children who receive MMR by 15 months of age	
	1 automated message sent	2 automated messages sent
0 personal attempts	20% ^C	35% ^B
1 personal attempt	50% ^A	65% ^{AB}

We calculated sample size needed per group to detect a difference for each of the contrasts below with alpha of 0.05 and power of 80%.

Contrast	Sample Size per Group
A vs C	36
B vs C	136
A vs. B	167
A vs. AB	167
B vs. AB	40
C vs. AB	16

To fully power the 2 X 2 factorial trial, we estimate needing 167 per group X 4 groups = 668 total subjects. There are currently 712 children eligible for the study. More will become eligible every month so we expect to far exceed the required sample size after 3 replications. If needed, we could increase the number of replications of the trial to reach the targeted sample size. We acknowledge that we are not powered to precisely estimate any interactions between interventions.

MyChart Trial:

In hypothesis testing for 0 message vs. 1 message vs. 2 messages, we will do the testing in a fixed sequence - test 2 messages vs. 0 message first, only if it is significant then test 2 messages vs. 1 message, thus the type I error rate of 0.05 is retained. Since the hypothesis testing of 2 messages vs. 0 message would be considered easier to achieve than the hypothesis testing of 2 messages vs. 1 message, the power analysis for this trial should be based on the design of (standard message vs. tailored message) by (1 message vs. 2 messages). We based our hypotheses (see table, below) on previous work indicating approximately 20% WCC appointment completion on automated text reminders. We anticipate that a tailored message increases the WCC appointment completion rate by another 10%.

Hypotheses		% of children complete WCC within 8 weeks	
		1 automated message sent	2 automated messages sent
Standard Message	2%	10% ^C	20% ^B
Tailored Message		20% ^A	30% ^{AB}

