We calculated sample size needed per group to detect a difference for each of the contrasts below with alpha of 0.05 and power of 80%.

Contrast	Sample Size per Group
A vs C	199
B vs C	199
A vs. AB	293
B vs. AB	293
C vs. AB	62

We assume no difference between A vs. B and thus not consider powering the comparison between these two groups, but we will explore non-inferiority analysis for this comparison in data analysis. To fully power the above contrasts, we estimate needing 293 per group X 4 groups = 1172 subjects. Adding 293 in the zero message group, we would need a total of 1465 subjects. There are currently 1000 children eligible for the study. More will become eligible every month so we expect to exceed the required sample size after 2 replications. If needed, we could increase the number of replications of this trial to reach the targeted sample size. We acknowledge that we are not powered to precisely estimate any interactions between interventions.

Televox (6-11yo) Trial:

We calculated sample size based on the following hypotheses:

% of children complete WCC within 8 weeks		
no message	2 Low Tailored Messages	2 High Tailored Messages
2%	20%	30%

With alpha of 0.05 and power of 80%, to fully power the contrasts between the above groups, we need 293 per group X 3 groups=879 subjects. Currently there are 2500 kids eligible, so we expect to reach the targeted sample size.

Televox (12-17yo) Trial:

We calculated sample size based on the following hypotheses:

% of children complete WCC within 8 weeks		
no message	2 Low Tailored Messages	2 COVID Tailored Messages
2%	30%	40%

With alpha of 0.05 and power of 80%, to fully power the contrasts between the above groups, we need 356 per group X 3 groups=1068 subjects. Currently there are 1100 kids eligible, so we expect to reach the targeted sample size.

Analysis

We will conduct descriptive analyses to characterize the participants in terms of demographics and other potential covariates in consideration (child age group, parent's preference for call vs. text mode of contact, whether parent had activated MyChart account, access to appointment, whether patient receipt of any past immunizations, historic no show rate, and community rates of COVID). We will use chi square tests to examine whether participants in the 4 groups are similar in these characteristics.

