For the Personal Contact (12-14 mo & 4 years old) trials, we will conduct intent-to-treat analyses using logistic regression models (without adjusting for covariates) for each of our three binary outcomes: completed appointment

within 2 weeks, completed appointment within 8 weeks, receipt of MMR by 15 months of age or receipt of 2nd MMR by 3 months after randomization. We will do pair-wise comparison among the 4 groups and adjust p value of each comparison for multiplicity. If participants in the 4 groups differ on potential covariates, we will conduct additional analyses adjusted for these variables.

For the MyChart and Televox Trials (6-17 years old), we will conduct intent-to-treat analyses using logistic regression models (without adjusting for covariates) for each of the binary outcomes: scheduled appointment within 2 weeks, completed appointment within 8 weeks, receipt of 1st dose of COVID vaccination (age 12-17 years) within 8 weeks, family member receipt of COVID vaccination within 8 weeks. We will do pair-wise comparison among the treatment groups and adjust p value of each comparison for multiplicity. If participants differ in potential covariates across treatment groups, we will conduct additional analyses adjusted for these variables. We will explore non-inferiority analysis for comparison the two groups that are expected to have similar appointment scheduled and completion rate in the MyChart trial.

We will also conduct per-protocol analyses according to the interventions actually received by the participants, recognizing that actual intervention received could be different from initial randomized intervention. For example, a parent allocated to group A might schedule an appointment after receiving the automated message and therefore would not receive a personalized contact attempt. In addition, we may explore potential interaction between the two interventions as a secondary analysis. All analysis will be conducted using SAS version 9.4.

Duration

The study will begin upon IRB approval and continue through December 31, 2022. During this time, we will discuss the significance of data, potential future projects and dissemination of results.

Process of Obtaining Consent

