Official Title of the study: **Effect of Varied Outreach Methods on Appointment Scheduling, Appointment Completion, and Receipt of MMR Vaccination**

NCT number: **NCT04567342**

Document name: **Statistical Analysis Plan**

Date of the document: **7/31/2023**

The results of the Outreach Methods study will be assessed as described in this document. This statistical analysis plan begins with an overview of the key components of the study, including its design, objectives, and outcomes measures. This is followed by a detailed description of the statistical analyses that will be utilized to address study hypotheses.

1. Overview of study: This study used a 2x2 factorial randomized control trial to test the impact of automated text/telephone messages and personal contact attempts on well child care (WCC) scheduling and completion and receipt of MMR vaccine. We randomized eligible patients to 1 of 4 groups: 1 automated message (Group 1), 2 automated messages (Group 2), 1 automated message plus personal contact attempts (Group 3), or 2 automated messages plus personal contact attempts (Group 4). We generated random allocation sequence stratified by clinic location using block randomization (with a block size of 4). Based on sample size calculations, we planned to enroll a minimum of 668 subjects overall aged 12-14 months old and 4 years old that met eligibility criteria based on data obtained from the electronic health record (EHR) from three academic pediatric primary care practices.

1.1 Study Objective: Test the effectiveness of text/telephone outreach messages and personal contact attempts on well child care (WCC) scheduling and completion and receipt of MMR vaccine.

Working hypothesis: Twenty percent of patients in Group 1, 35% of patients in Group 2, and 50% of those in Group 3, and 65% of those in Group 4 would receive the MMR vaccine by 15 months of age (for children who were 12-14 months old) or receipt of the second MMR dose by 3 months after first intervention (for children 4 years old).

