2.3.2 Primary outcome analysis

Primary outcome: Receipt of MMR by 15 months of age (for children who were 12-14 months old) or receipt of the second MMR dose by 3 months after first intervention (for children 4 years old).

- Receipt of MMR (yes or no) based on electronic health record documentation

For the primary outcome, we will use a modified Poisson regression models to estimate risk ratio (RRs) with statistical significance defined as 2-sided $p < .05$. If participants differ in potential covariates across treatment groups, we will conduct additional analyses adjusted for these variables.

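### The Personal Contacts trial is a 2x2 factorial, but no planned analysis estimates either factor from all 668 children, and the stated 80% power does not survive the planned multiplicity adjustment

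*Protocol*

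**What the plan says.** The SAP overview describes the design in factorial terms: "This study used a 2x2 factorial randomized control trial to test the impact of automated text/telephone messages and personal contact attempts". The protocol (Design/Method, factors under study) lays out the same two-by-two table.

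Under Power/Sample Size, the protocol sizes the trial cell against cell: "We calculated sample size needed per group to detect a difference for each of the contrasts below", each at alpha 0.05 and 80% power. The six results are 36, 136, 167, 167, 40 and 16 per group. The largest sets the total: "To fully power the 2 X 2 factorial trial, we estimate needing 167 per group X 4 groups = 668 total subjects". The same section accepts that interactions are not powered.

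The protocol's Analysis section specifies logistic regression and then: "We will do pair-wise comparison among the 4 groups and adjust p value of each comparison for multiplicity". It does not name the adjustment method. Interaction is an optional secondary analysis.

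SAP 2.3.2, for the primary outcome, says only that "we will use a modified Poisson regression models to estimate risk ratio (RRs", with "statistical significance defined as 2-sided" at the 0.05 level. It names no pairwise contrast, no main effect and no multiplicity adjustment.

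**The concern.** A factorial design lets every child contribute to the estimate of each factor. A cell-versus-cell comparison uses 334 of the 668. If the two factors act roughly additively, as the planning rates assume, the planned comparisons leave half the information on each factor unused and spread two questions over six tests.

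The power statement raises a second problem. The 167 per group is calculated at alpha 0.05 for each contrast, yet the analysis adjusts the p values of those same contrasts. The stated 80% therefore belongs to a test that the protocol does not plan to use.

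At stake is whether the trial can show that a second automated message helps, and how precisely it can say so.

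**Working it through.** **Inputs.** Planning rates (protocol hypotheses table; SAP 1.1): C = 20% (one message, no contact), B = 35% (two messages, no contact), A = 50% (one message, contact), AB = 65% (two messages, contact). There are 167 per cell. Alpha is 0.05, two-sided per the SAP; the protocol's sizing text does not state sidedness. No dropout allowance is stated, so none is applied.

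**Reproducing the plan's figures.** With unpooled variance, n = (1.960 + 0.842)² × [p1(1−p1) + p2(1−p2)] / d².
- A vs AB: 7.849 × (0.2500 + 0.2275) / 0.15² = 166.6, so 167.
- B vs C: 7.849 × (0.2275 + 0.1600) / 0.15² = 135.2, so 136.
- The other four give 35.8, 166.6, 39.7 and 15.02, which round up to the stated 36, 167, 40 and 16.

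All six agree.

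**Power of the two message contrasts at 167 per cell.** Power = Φ(d/SE − z), with z = 1.960 unadjusted and 2.638 for Bonferroni over six.
- A vs AB: SE = √(0.4775/167) = 0.0535 and d/SE = 2.805. Power is 80.1% unadjusted and 56.6% with Bonferroni.
- B vs C: SE = √(0.3875/167) = 0.0482 and d/SE = 3.114. Power is 87.6% unadjusted and 68.3% with Bonferroni.

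The pooled-variance formula gives slightly lower Bonferroni values (55% and 67%). In a simulation of 40,000 trials, Tukey gave 58% and 69%, and Holm 77% and 84%.

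**Message main effect, all 668 children.** The effect is the average of (B − C) and (AB − A), which is 15 points. Its SE is ½√[(0.1600 + 0.2275 + 0.2500 + 0.2275)/167] = ½√(0.865/167) = 0.0360, so d/SE = 4.168.
- Power at alpha 0.05: Φ(4.168 − 1.960) = 98.6%. Collapsing over contact (35% vs 50%, 334 vs 334) gives 97.6%. A simulated logistic model with both factors gave 98.4%.
- Power at alpha 0.025 for each of two factors: 97.3% stratified, 95.5% collapsed.

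**Precision.** The 95% half-width for A vs AB is 1.96 × 0.0535 = 10.5 points. For the main effect it is 1.96 × 0.0360 = 7.1 points.

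**Personal contact factor.** A vs C and B vs AB (30 points each) have more than 99.9% power unadjusted. So does the main effect (27.5% vs 57.5%). The half-width falls from 1.96 × √(0.410/167) = 9.7 and 1.96 × √(0.455/167) = 10.2 points to 7.1.

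**Scale.** The planned message effect is +15 points in both rows. As a risk ratio it is 35/20 = 1.75 without contact and 65/50 = 1.30 with it. The planning cells are therefore additive on the risk-difference scale but not constant on the SAP's risk-ratio scale.

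**The case against.** The pairwise plan has a real rationale. A vs B asks whether one message plus a contact attempt beats two messages without one. That is a choice between strategies with different staff costs, it is a listed contrast, and it needs 167 per group by itself. The protocol's background also calls for evidence on combinations of reminders. Neither main effect answers that question. This stands, and the pairwise comparisons should stay.

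Additivity is only assumed. The protocol withholds further outreach from parents who schedule first, so the contact effect may depend on how many messages went before. The interaction SE is twice the main-effect SE, 2 × 0.0360 = 0.0720, a half-width of 14.1 points, so the trial can check this only roughly. This also stands: a main effect may be an average of unequal effects.

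Four stronger readings are tempting, and the documents do not support them.
- *Both factors lose power.* Only the message factor does.
- *A second-message effect below 15 points would probably be missed.* Unadjusted, A vs AB still has 74% power at 14 points and 60% at 12. At 15 points the chance that at least one of the two message contrasts is significant is 1 − 0.199 × 0.124 = 97.5% unadjusted.
- *The trial is twice as large as needed.* The message main effect alone would reach 80% power with about 304 to 340 children (76 to 85 per cell), but A vs B would then have only 47% to 52%.
- *The SAP plans pairwise testing.* It does not say so. The pairwise plan rests on the protocol, and the SAP leaves the contrasts open.

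**Conclusion.** The point holds as a limited, inexpensive improvement. The trial is described as a factorial, but it is sized and, in the protocol, analysed only by cell comparisons. Neither document plans an estimate of either factor from all randomised children.

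For the second message, the stated 80% is correct for the weaker contrast before adjustment. Under the planned adjustment it becomes about 55% to 77%, depending on the unnamed method. The main effect has about 98% power and an interval about one third narrower (7.1 vs 10.5 points). For personal contact the gain is precision only.

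These figures rest on the plan's own cell rates, 167 children per cell and no dropout. The main-effect power also assumes that averaging over the other factor is meaningful, which the planning rates support on the risk-difference scale. Nothing here shows that 668 was the wrong size or that pairwise comparison is invalid.

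**What to change.** 1. In the protocol's Analysis section and SAP 2.3.2, add two named contrasts: two vs one message, and contact vs none. Estimate both from one model containing both factor indicators, and state the alpha for the pair (for example 0.025 each).
2. Report the risk difference alongside the SAP's risk ratio, and the interaction with its confidence interval.
3. Keep the pairwise comparisons, including A vs B, and name their multiplicity adjustment. Reconcile the two documents, since the protocol adjusts and the SAP is silent.
4. In Power/Sample Size, restate the power of 668 for the two main effects and for the adjusted pairwise contrasts.

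This costs wording and a few extra model outputs, and needs no new data. The downside is interpretive: if the factors interact, each main effect is an average and must be read with the cell results. SAP 2.2.1 gives a study end date of 8/6/21 and the SAP is dated 7/31/2023, so if outcomes have been seen, the added contrasts should be labelled post hoc.

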PPC	
Hi, this is [Staff First Name] from PPC. [Pt first name] is due for a check up. I'll call in a day or two to help schedule that appointment or you can walk in today to have your child seen! You can also call [contact], option 1 to schedule.
	
Hi, this is [First Name] from PPC. I noticed that [Child's First Name] is due for a check up. Can I schedule that for your right now?
 
Alternate script for leaving a voice message: Hi, this is [First Name] from PPC. I noticed that [Child's First Name] is due for a check up. Sorry I missed you. Please call [contact], option 1 to schedule your appointment or walk in today to have your child seen.

*Scripts have been translated into Spanish versions by Interpreter Services

Response variables (outcomes):

- Appointment **was scheduled** within 2 weeks of intervention (Y/N) (date of actual appointment may be greater than 2 weeks from intervention)
- Appointment **was completed** within 8 weeks of intervention (Y/N). Appointment completed within 8 weeks of randomization will be used for group who does not receive any intervention.
- (Primary Outcome) Receipt of MMR by 15 months of age or receipt of 2nd MMR dose by 3 months after randomization (Y/N)
- Receipt of 1st COVID vaccination (ages 12-17 years) within 8 weeks of first intervention (Y/N)
- Family member receipt of COVID vaccination in our health system within 8 weeks of first intervention

Blocking: (controlling for factors that might influence the outcome)

- Age (12-14 months, 4 years)
- Clinic location (PPC, HPC, FPC)

Personal Contacts (12-14 months & 4-year-olds) Trial:

Randomization: Eligible patient will be identified by running a report in the electronic health record (EHR). We will run this report, stratified by clinic location, and randomly assign patients into one of the four groups created by our 2 X 2 design. Groups will receive their assigned intervention in one of four successive weeks with the sequence randomly assigned (see table below).

Replication: We will conduct a total of 3 trials, repeating the randomization procedure every 4 weeks to identify children who become eligible: Weeks 1-4 = trial #1, weeks 5-8 = trial #2, weeks 9-12 = trial #3.

	1 automated message sent	2 automated messages sent
--	---------------------------------	----------------------------------

0 personal contact attempt	Message sent on Thu (weeks 3, 5, 10)	Message sent on Thu & Fri (weeks 4, 6, 12)

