1 personal contact attempt	Above plus attempt Mon – Fri of following week (weeks 2, 7, 11)	Above plus attempt Mon – Fri of following week (weeks 1, 8, 9)

MyChart and Televox Trials (6-17 years old):

Randomization: Eligible patients will be identified by running a report in the electronic health record (EHR). We will run this report, stratified by clinic location, and randomly assign patients into one of the study groups as described above. Groups will receive their assigned intervention in one of four successive weeks with the sequence randomly assigned (see table below).

We will randomize children who are eligible and implement interventions for each trial : Weeks 1-3 = Televox Trial 12-17yo, Weeks 4-7 = Televox Trial 6-11yo, Weeks 8-10 = MyChart Trial.

MyChart Trial:

	no message	1 MyChart message sent	2 MyChart messages (e.g. Mon and Thurs)
Standard Message	No intervention	Week A	Week B
Tailored Message		Week A	Week B

Televox (6-11yo) Trial:

no message	Low Tailored Message 2 automated standard messages sent (e.g. Thu, Fri) (weeks C, C)	High Tailored Message 2 automated tailored messages sent (e.g. Thu, Fri) (weeks D, D)
-------------------	---	--

Televox (12-17yo) Trial:

no message	Low Tailored Message 2 automated tailored messages sent (e.g. Thu, Fri) (week A)	COVID Tailored Message 2 automated messages sent (e.g. Thu, Fri) (week B)
-------------------	---	--

Of note, automated messages and/or personal contact attempts will not be completed if the parent schedules an appointment after being randomized but before receiving the intervention.

Covariates for logistic regression: (factors that might influence the outcome if not be balanced across groups)

1. Child age at the time of randomization (rationale: visits are less frequent for children age 4 years)
2. Parent preference for call vs. text mode of contact (rationale: calls may be more likely to get blocked than texts)
3. Parent with activated MyChart account (Y/N) (rationale: not dependent on calling scheduling center to make appointment)
4. Access to appointment: Number of days to 3rd next available appointment at patient's clinic at time their first automated message is sent
5. Patient receipt of any past immunizations (Y/N) (rationale: vaccine refusing parents will be unlikely to change even if they return for well child check)

6. School-age vs. adolescent patient age (rationale: adolescents less likely to get yearly check-ups)
7. Historical no-show rate

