1.2 Outcome measures

Primary

- Receipt of MMR by 15 months of age (for children who were 12-14 months old) or receipt of the second MMR dose by 3 months after first intervention (for children 4 years old).
 - Receipt of MMR (yes or no) based on electronic health record documentation

Secondary

- Well-child visit scheduled within 2 weeks of receiving first intervention
 - Appointment scheduled (yes or no) based on electronic health record documentation
- Well-child visit completed within 8 weeks of receiving first intervention
 - Appointment completed (yes or no) based on electronic health record documentation

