2.3 Statistical Report Contents

The following section outlines the contents of the final statistical analysis. For all analyses, subjects who are enrolled in the study and are eligible will be analyzed in the groups to which they were allocated.

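### The protocol's supplementary per-protocol analysis groups children by outreach received, which depends on scheduling, itself an outcome; it still stands for MyChart and Televox

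*Protocol*

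**What the plan says.** The protocol's Analysis section plans intent-to-treat logistic regression for Personal Contacts and, separately, for the other trials: "For the MyChart and Televox Trials (6-17 years old), we will conduct intent-to-treat analyses using logistic regression models". It then adds: "We will also conduct per-protocol analyses according to the interventions actually received by the participants". Its one example of a departure from allocation is that "a parent allocated to group A might schedule an appointment after receiving the automated message and therefore would not receive a personalized contact attempt".

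The example follows from a design rule. The note after the protocol's randomization tables says that automated messages and personal contact attempts "will not be completed if the parent schedules an appointment after being randomized but before receiving the intervention".

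Scheduling is also an outcome. The protocol's list of response variables includes scheduling within 2 weeks of intervention, and SAP section 1.2 has "Well-child visit scheduled within 2 weeks of receiving first intervention" as a secondary outcome. (The protocol's Analysis section refers to completion within 2 weeks for Personal Contacts, but its own outcome list and the SAP both say scheduling.)

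The Personal Contacts timetable gives "Message sent on Thu (weeks 3, 5, 10" for one message without contact, and "Above plus attempt Mon – Fri of following week (weeks 2, 7, 11" for one message with contact.

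SAP section 2.3 says: "For all analyses, subjects who are enrolled in the study and are eligible will be analyzed in the groups to which they were allocated". The SAP (version 1.1, 7/31/23) is later than the protocol (version 1.1, 1/14/22), describes only the Personal Contacts 2x2 trial, and lists no as-received analysis.

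**The concern.** An analysis by intervention received needs receipt to be unrelated to prognosis. Here the protocol itself ties receipt to scheduling. A parent who responds to the first message never gets the personal contact, so the children who did get it are those who had not yet responded. That is an as-treated comparison, although it is called per-protocol.

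A child whose contact is withheld because a visit was booked after the first message followed the assigned strategy exactly. The protocol does not say whether such a child is moved to the lighter arm or dropped. For scheduling within 2 weeks of the first message, this child is a success. Either treatment therefore takes successes out of the intensive arm, and moving also adds them to the lighter arm. A contact with no effect would look harmful.

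The result would sit beside intent-to-treat under a label that readers tend to trust, in a study meant to guide how outreach resources are allocated.

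**Working it through.** **Inputs from the documents.** Personal Contacts: 167 per group; assumed MMR 20% (C, one message) and 50% (A, one message plus contact). MyChart, standard message: completion 10% (one message) and 20% (two), 293 per group. Televox 6-11 years: completion 2% (none) and 20% (low tailored), 293 per group. The 167 reproduces with unpooled variances for 50% vs 35%: (0.25 + 0.2275) × (1.960 + 0.842)² / 0.15² = 166.6, rounded up to 167. The sample sizes are not in dispute.

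**Assumed.** The documents give no rate of early scheduling. Let s be the share of the intensive arm whose step is withheld because a visit was scheduled, and q the share of those children who reach the outcome.

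**Formulas.** Intensive arm rate p1, lighter arm rate p0, equal n.
- Moved: p1' = (p1 - sq)/(1 - s) with n(1 - s) children; p0' = (p0 + sq)/(1 + s) with n(1 + s).
- Dropped: p1' as above; p0 unchanged.
- Tests are pooled two-sided z tests, unadjusted.
- Both arms get the same first message, so sq should not exceed p0.

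**Timing.** Thursday to the following Monday is 4 days, and to the following Friday 8 days. If scheduling is spread evenly over 14 days, 4/14 = 29% to 8/14 = 57% of it comes before the contact.

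**Scheduling, Personal Contacts, no true effect, 20% in both arms (q = 100%, since these children schedule after the first message).**

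| Contact day | s | Moved | Dropped |
|---|---|---|---|
| All Monday | 0.20 × 4/14 = 5.7% | 15.2% vs 24.3%: -9.2 points, p = 0.036 | 15.2% vs 20%: -4.8, p = 0.25 |
| All Friday | 0.20 × 8/14 = 11.4% | 9.7% vs 28.2%: -18.5 points, p < 0.001 | 9.7% vs 20%: -10.3, p = 0.011 |

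Differences are taken before rounding. With 10% scheduling in both arms, moving shows -5.1 to -10.3 points; with 30%, -12.1 to -24.7. If contact truly raises scheduling from 20% to 50%, the 30 points become 22.6 to 15.3 (moved) or 27.0 to 23.5 (dropped).

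**MMR, A vs C (50% vs 20%), same s, moved.**
- q = 25%: 31.2 to 32.7 points, above the true 30.
- q = 50%: 28.4 to 26.9.
- q = 75%: 25.5 to 21.1.
- q = 100% (upper bound): 22.6 to 15.3, with p = 0.0035 at the lowest.

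All remain significant. For small s, moving works against the intensive arm when q > (p1 + p0)/2, here 35%; dropping does so when q > p1, here 50%.

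**MyChart completion, standard message, two vs one, only if the withholding rule covers a second MyChart message.** As allocated: 10 points, p = 0.0007. Monday to Thursday is 3 days. With 10% scheduling within 2 weeks, s = 0.10 × 3/14 = 2.1%. Moved with q = 50%: 19.3% vs 10.8%, which is 8.5 points, p = 0.004.

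**Televox 6-11 years, low tailored vs none, s = 1%, q = 50%, moved.** 19.7% vs 2.5%: 17.2 points instead of 18.

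**The case against.** The strongest reply is that little depends on this analysis. Intent-to-treat is planned for every trial, no decision rule uses the as-received result, and the protocol openly notes that received and allocated interventions may differ. For Personal Contacts, the later SAP analyses everything as allocated and lists no such analysis, so the largest figures above come from the one trial where the plan has already dropped it. All of this stands, and it makes the point secondary. It does not settle MyChart and Televox, which the SAP does not cover.

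The rates are assumed, and the -18.5 end needs every contact to fall on Friday. That also stands. The dependence of the grouping on scheduling does not rest on the rates.

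Three stronger readings are tempting, and the documents do not support them.
- A reader might infer that every child whose outreach is withheld is a scheduling success by definition. The rule also covers parents who schedule before any message. Those children have no intervention date, and both documents count the 2 weeks from intervention, so their outcome is unclear.
- A reader might infer that the MyChart comparison would lose significance. At q = 50% that needs s of about 6.0%. With even timing this means 0.0604 × 14/3 = 28% scheduling within 2 weeks. If half of those completed, completion would be about 14%, above the protocol's 10% for that arm. The timing-based case stays significant.
- A reader might infer that the bias always runs against the intensive arm. For completion and MMR it can run either way.

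**Conclusion.** The concern holds as a secondary point. Grouping by intervention received depends on an outcome, so the planned comparison is as-treated and randomization does not protect it.

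For scheduling within 2 weeks of the first message, the bias is against the more intensive arm among children who schedule after that message. It could be large in the Personal Contacts illustration: -9.2 to -18.5 points moved and -4.8 to -10.3 dropped, with no true effect. This rests on 20% scheduling in both arms, even spread over 14 days, and contacts all on Monday or all on Friday. For MMR, A vs C stays significant in every scenario shown. For MyChart the timing-based change is 10 to 8.5 points, if the withholding rule applies there; for Televox it is small.

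The intent-to-treat analyses are unaffected. For Personal Contacts the protocol needs only to be reconciled with the SAP. For MyChart and Televox the as-received analysis still stands.

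**What to change.** - **MyChart and Televox:** either delete the as-received analysis, or keep children in their randomized arms and count a step withheld because a visit was already scheduled as adherent to the assigned strategy.
- **If an as-received analysis is still reported:** label it exploratory and as-treated, say whether children with a withheld step are moved or dropped, and state the resulting bias.
- **Personal Contacts:** align the protocol's Analysis section with SAP section 2.3, so that both documents analyse as allocated.

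The cost is one or two sentences and no new data. The downside of deletion, or of keeping children in their randomized arms, is that there is no separate estimate by intervention received.
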